### 8.3. COHORT B TO COHORT A TRANSITIONS

If at any time during the study period a Cohort B participant develops active TB disease, he/she would be approached for consenting to be part of Cohort A. After the consent process, if he/she were to agree then a new SIN would be assigned with the Cohort A identifier. All Cohort B visits would cease and the participant would follow the schedule of evaluations for Cohort A, with the exception of the data that has already been collected for the household. The eMOCHA system would auto-fill information that does not need to be repeated in order to minimize the burden on the participant.

## 9. STATISTICAL CONSIDERATIONS

### 9.1. SAMPLE SIZE AND ANALYSIS PLAN

**Aim 1.** The Active TB Cohort will include 800 adult PTB cases, 200 adult EPTB cases and 200 pediatric TB cases. The primary analysis set will be 800 adult PTB patients. Secondary analysis sets will include EPTB and pediatric TB.

Primary outcome is poor treatment outcome defined as failure, recurrence or death. Secondary outcomes will include time to AFB smear negativity, time to sputum culture negativity; time to detection of MGIT positivity. Host factors age, sex, DM, HIV, IAP exposure, tobacco exposure, malnutrition, and mental health will be key predictors for poor treatment outcomes.

Person-years of follow-up will be calculated for each member of the analysis set. Of TB patients who experience the outcome of interest, person-years of follow-up will be calculated as number of years between date of enrollment and date of event. Among those without the outcome person-years will be the number of years between enrollment and last date of follow-up. Crude treatment failure rates and 95% exact Poisson confidence intervals in the presence and absence of primary risk factors will be calculated. Adjusted treatment failure rate ratios will be estimated using multivariate Poisson regression models with person-years of follow-up as an offset. The Poisson regression models will also investigate interaction between individual and HH factors that might influence treatment outcomes.

A secondary subgroup analysis (may not be sufficiently powered) by enrollment sites, NIRT and BJMC, will be performed by adjusting the level of significance using a Bonferroni adjustment.

**Aim1 Power.** For Aim 1, we expect 20% (n=160) of 800 adult PTB cases will have the composite primary outcome (2% will fail, 6% will die, and 12% will have recurrence). This study will have at least 90% power at 5% level of significance to identify host and microbial risk factors (enumerated in section 3B3), with a prevalence of 10% - 40%, associated with poor treatment outcomes with relative risk ratio ranging from 1.5 to 6.0 over 24 months of follow-up.

**Aim 2.** The analysis set is individuals in the HH Contact Cohort: 3200 HH contacts of 800 PTB patients.

The primary outcome is diagnosis of active TB among individual HH contacts within 24 months of follow-up. Index PTB cases from the Active TB Cohort will form clusters and individuals within the HH of the index case are correlated. The association between host and microbial factors with progression from infection to active TB disease will be estimated using random effects.

Poisson regression models with index PTB cases as random effects. Random effects models will address the correlation of individuals within the HH. Relative risk ratios and 95% confidence intervals for host and microbial factors will be estimated from the models and will have a cluster-specific interpretation.

**Aim 2 Power.** We expect approximately 3200 HH contacts will be followed for an average duration of 2 years. We anticipate 85% (n=2720) of them will be HH contacts of a smear positive PTB case, 15% (n=480) will be contacts of a smear negative PTB. We estimate that at least 40% (n=1280) will be latently infected. We estimate that 320 (25%) of them would be recently infected and have a 15% 2 year risk of developing active TB. This would result in 48 active TB cases. We expect a background rate of active TB (regardless of latent TB infection) 0.37% per year, yielding an additional 24 cases. This yields an estimated 72 incident active TB cases.

**Aim 3.** The analysis set will be HH members of index PTB cases.

Primary outcome will be incident infection will be defined as positive TST or QGIT in children < 5 years or seroconversion of TST or QGIT among HH contacts. Secondary outcome will be prevalent or active TB with same MTB MIRU genotype.

Within household transmission rates will be calculated. Risk factor and covariate information collected on HH contacts will be used in the analysis. In addition the analysis will be adjusted for independent variables measured at HH level. A multivariate random effects Poisson regression model will be used to estimate the adjusted relative risk of MTB transmission to HH contacts in presence of host and microbial factors. The model will be adjusted for enrollment site (NIRT & BJMC).

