## PROTOCOL SUMMARY

TITLE	:	C-TRIUMPh: Cohort for TB Research by the Indo-US Medical Partnership
DESIGN	:	Multi-centric Prospective Observational Study
POPULATION	:	
 
(i) Active TB Cohort (Cohort A): 1200 adults and children with active TB (800 adults with newly diagnosed PTB starting Category I Rx (85% being AFB smear or Gene Xpert positive) + 200 adults with EPTB +200 children with TB)
 
(ii) Household (HH) Contact Cohort (Cohort B): 3200 adult and children -house hold contacts of the adults with active PTB
 
(iii) Control Cohort (Cohort C): 300 adults and 200 children – without a h/o of known TB contact100 households.
 
 
Each site will enroll approximately 50% of the sample

STUDY SITES	:	
 
(i) National Institute for Research in Tuberculosis (NIRT), Chennai
 
(ii) Byramjee Jeejeebhoy Medical College CTU (BJMC), Pune
 

FOLLOW UP DURATION	:	
 
(i) Active TB Cohort: Each participant will be followed up for 24 months
 
(ii) Household Contacts cohort: Each participant will be followed up for 24 months
 
(iii) Control Cohort: Each participant will be followed up for 12 months
 
 
C-TRIUMPh will undertake both epidemiologic/clinical and basic laboratory research studies that will address three specific aims -
 
Aim 1: To measure the host and microbial factors associated with TB treatment outcomes in Indian adults and children (Active TB cohort)
 
Aim 2: To investigate the host and microbial factors associated with progression from infection to active TB disease in adults and children. (Household Contacts)
 
Aim 3: To explore the host and microbial factors associated with TB transmission. (Household Contacts and Control Cohorts)

OBJECTIVES	:	

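### The Aim 1 site subgroup analysis is planned as Bonferroni-adjusted significance testing with no factor-by-site test, so it cannot show whether an effect differs between NIRT and BJMC

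*Protocol*

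**What the plan says.** Protocol section 9.1 gives the site analysis for Aim 1 one sentence. It begins "A secondary subgroup analysis (may not be sufficiently powered) by enrollment sites, NIRT and BJMC" and goes on to say that the analysis "will be performed by adjusting the level of significance using a Bonferroni adjustment". It does not state the number of comparisons behind the adjustment, the resulting significance level, the model, or the conclusion the analysis is meant to support.

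The only interaction named for Aim 1 is a different one: "The Poisson regression models will also investigate interaction between individual and HH factors that might influence treatment outcomes". Site appears once more in section 9.1, under Aim 3, as a covariate: "The model will be adjusted for enrollment site (NIRT & BJMC".

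On size, section 9.1 states "The primary analysis set will be 800 adult PTB patients", and the Protocol Summary adds "Each site will enroll approximately 50% of the sample".

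**The concern.** A significance level is adjusted only for significance tests, so the natural reading is that the risk factors are tested separately in each site at a reduced level. The null hypothesis of each such test is that the rate ratio equals 1 in that site. Whether an association differs by site has another null hypothesis: that the two site-specific ratios are equal. The protocol names no test of it.

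The gap matters if the two results are set side by side. With half the patients in each analysis, a factor that acts equally at both sites can easily be significant at one and not at the other. A reader may then take it for a site-specific risk factor. The two sites recruit differently (section 4.4: primary health centres in two TB units of Tiruvallur district, and a medical college in Pune with inpatient wards and an HIV treatment centre), so a chance contrast could look plausible.

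**Working it through.** **Inputs from the protocol.** 800 adult PTB patients, 20% with the composite outcome, factor prevalence 10-40%, RR 1.5 to 6.0 (section 9.1); about half the sample at each site (Protocol Summary). The event count reproduces: 2% + 6% + 12% = 20%, and 0.20 × 800 = 160. Per site this is 400 patients and 80 events. The stated power of at least 90% concerns the pooled analysis; no power is given for the site analysis.

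**Assumptions.** Two-sided tests; a divisor of 2 for two sites, so a level of 0.05/2 = 0.025. As a sensitivity case, the eight host factors listed in section 9.1 tested at two sites give 16 tests and a level of 0.05/16 = 0.0031.

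**Formulas.** With prevalence f and overall risk 0.20, the unexposed risk is p0 = 0.20/(1 − f + f·RR) and the exposed risk is p1 = RR·p0. Within-site power P comes from the two-proportion test with pooled variance under the null. If the true effect is the same at both sites, the chance of significance at exactly one is 2P(1 − P).

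**Example (f = 20%, RR 1.5, level 0.025).** p0 = 0.20/1.1 = 0.1818; p1 = 0.2727; 320 unexposed and 80 exposed patients.
- Null standard error: √(0.16 × (1/320 + 1/80)) = 0.0500.
- Alternative standard error: √(0.1818 × 0.8182/320 + 0.2727 × 0.7273/80) = 0.0543.
- P = Φ((0.0909 − 2.241 × 0.0500)/0.0543) = 0.348.
- Exactly one site significant: 2 × 0.348 × 0.652 = 0.454.

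**Range over prevalence 10-40%, identical true effect at both sites**

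| RR | Within-site power, level 0.025 | Exactly one site, level 0.025 | Exactly one site, level 0.0031 |
|---|---|---|---|
| 1.5 | 23-42% | 36-49% | 16-30% |
| 1.75 | 45-71% | 41-49% | 35-50% |
| 2.0 | 66-89% | 20-45% | 42-49% |
| 2.5 | 92-99% | 2-15% | 10-34% |
| 3.0 | 99% or more | at most about 2% | 1-9% |

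A simulation of the within-site Wald tests at 0.025 agrees closely: 39-49%, 41-50%, 20-43%, 2-13% and at most about 2%. In the same simulated data a factor-by-site test at 5% rejects in about 4-5% of studies using the log-RR variance, and in 1-3% using the model-based Poisson variance.

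**Role of Bonferroni.** 2P(1 − P) peaks at P = 0.5, so a stricter level can move discordance either way. Going from 0.05 to 0.025 lowers it at RR 1.5 (prevalence 10%: 43% to 36%) and raises it at RR 2.0 (prevalence 20%: 20% to 28%).

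**The case against.** The strongest defence is that the protocol never says it will contrast the sites. No aim or hypothesis concerns site differences, and estimating within each site under multiplicity control is a coherent, if limited, secondary analysis. That stands in part: the discordance figures describe an error only if someone compares the two results. Subgroup results are usually read that way, however, and the sentence offers no other purpose.

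A second defence is that the model for a secondary subgroup analysis belongs in the SAP, which is not at hand. An SAP could add an interaction term. But the protocol has already fixed the inferential method in section 9.1, and an SAP that follows it would inherit the gap.

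Third, the protocol concedes that power may be insufficient. This lowers the weight of the point without removing it, because low within-site power is what produces one-site-only results, and the caveat does not warn against reading them as differences.

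Four stronger readings are tempting, and the documents do not support them:
- That the study will report false site-specific risk factors. No such claim is planned.
- That Bonferroni is the cause or always makes matters worse. The direction depends on the effect size, as shown above.
- That the problem holds across the protocol's whole RR range of 1.5 to 6.0. With a divisor of 2 it has nearly gone by RR 3.
- That the contrast is one of rural against urban patients. Section 4.4 does not call the Tiruvallur population rural.

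**Conclusion.** The point holds, as a minor one. As written, the site analysis can address whether a factor has an effect within a site, but not whether the effect differs between sites, and the protocol names no other test that could. If the site results are compared, equal effects would look different in roughly 20-49% of studies for RR between 1.5 and 2.0, and seldom from RR 3 upward. The lower effect sizes are relevant to this study: 1.5 is the bottom of the protocol's own range, and section 2.2 cites a pooled RR of 1.89 for diabetes and mortality.

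The sizes rest on equal site enrolment, a 20% outcome at each site, two-sided tests and a divisor of 2. The divisor is an assumption, not a protocol figure; with 16 tests the discordance is lower at RR 1.5 and higher at RR 2.0 and 2.5. The cause is low within-site power, which the Bonferroni adjustment does not address. The pooled Aim 1 analysis of 800 patients is unaffected.

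**What to change.** Replace the sentence in section 9.1 with one pooled Poisson model on the 800 adult PTB patients that contains site and a factor-by-site term. Report the ratio of rate ratios between sites with its 95% CI. Show the site-specific rate ratios with 95% CIs descriptively, without significance claims within a site. If a multiplicity adjustment is kept for the interaction tests, state how many comparisons it covers.

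The cost is one rewritten sentence and no extra data. The downside is that the interaction test also has limited power: for RR 1.0 at one site and 2.0 at the other, simulation gives about 38-68% with the log-RR variance and 27-59% with the Poisson variance. The text should therefore say that a non-significant interaction is not evidence of equal effects and that the confidence interval carries the information.

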### 2.2. FACTORS ASSOCIATED WITH POOR TB TREATMENT OUTCOMES

Relative impact of potentially modifiable host factors (e.g. HIV, DM, smoking, IAP, alcohol misuse, under-nutrition, mental health status) on treatment outcomes such as failure, recurrence or death is not well established in populations including Indians. While most patients treated for TB are cured of TB, poor outcomes such as treatment failure, recurrent disease and death remain important challenges. Approximately 85% of Indian patients who are treated for active smear-positive PTB via the Directly Observed Therapy Strategy (DOTS) are cured (AFB smear and culture negative). However, 2% fail (remain smear positive at 5 months of treatment), 6% die on treatment, and the remainder default or transfer out. Furthermore, approximately 12% of cured patients develop recurrent TB within 18 months of treatment, either due to relapse of the same strain or re-infection from others in the community. A patient's second course of TB treatment is more than twice as likely to fail, and more than 4 times as likely to involve MDR-TB. As shown in *Table 1*, poor treatment outcomes are linked to potentially modifiable host factors though with variable quality of evidence and estimations of individual contributions.

**HIV** has clearly been shown to increase TB treatment failure, death and recurrence and low CD4 counts increase that risk further [2,3]. While HIV is an important risk factor at the individual level, it is not likely to be a primary driver of poor treatment outcomes in India's TB epidemic as only 0.3% of India's population has HIV and only 2-15% of Indian patients with TB have HIV co-infection.

Though **Diabetes Mellitus (DM)** increases risk of TB two-fold compared to 22 times for HIV, DM is estimated to account for at least 20% of smear positive PTB cases in India [4-6], making it a more relevant risk factor in this setting. Most but not all data suggest that DM is associated with reduced 2-3 month sputum conversion, increased mortality (pooled RR of 1.89 based on 23 studies) [7] and may be a risk factor for TB recurrence and relapse (RR of 3.89) [7] but few studies have adjusted appropriately for confounders. It is unknown if DM is associated with acquired drug resistance.

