**TABLE 1: SCHEDULE OF EVALUATIONS FOR ACTIVE TB COHORT**

CRF   Time	Entry	2W	4W	8W	5M	6M	12M	18M	24M	End of Tx	TB recurrence (failure, relapse)
Consent/Enrollment	X										
Medical History	X										
Psychosocial Interview	X			X		X	X	X		X	X
Socio-demographic Interview	X										
Clinical Assessment (i.e. TB and Lung Health Assessment, Physical examination  , Concomitant Meds, Diagnoses/AEs)/ Medication History	X	X	X	X	X	X	X	X	X	X	X
TB Medication Adherence	X	X	X	X	X	X				X	
Nutrition Assessment 	X					X				X	X
Anthropometrics 	X	X	X	X	X	X	X	X	X	X	X
Chest Radiograph 	X			X		X					X
Sputum AFB and culture X 2 (DST if culture+) 	X	X	X	X	X	X		X		X	X
Sputum for Cepheid Gene-Xpert X 2	X										X
Extrapulmonary TB sample for AFB and culture/histopathology	X 										X
Hematology (CBC)	X			X							X
HIV Test (if not already known)	X										X
CD4 count if HIV +ve 	X										X
Hemoglobin A1c (Adults) 	X									X	X
LFT	X		X	X						X	X
Chemistry (Renal panel, glucose)	X									X	X
Urinalysis	X										X
Urine Pregnancy test	X			X		X					X
PFT (Adults), Spirometry (Child) (random subset)				X						X	X
Samples for Biorepository	Entry	2W	4W	8W	5M	6M	12M	18M	24M	End of Tx	TB Recurrence
Stored Plasma sample for PK 			X		X						
Stored Plasma	X		X	X		X	X		X	X	X
Whole Blood for DNA				(X) 							
Stored Sputum	X	X	X	X		X				X	X
Stored Urine	X		X	X		X	X		X	X	X

Stored Hair	X		X		X	X				X	X
Stored Mtb isolate	X			X	X	X					X
Whole Blood for Host mRNA (PAXgene)	X		X	X		X	X		X	X	X
Whole Blood forPBMC	X		X	X		X	X		X	X	X
Whole blood for Quantiferon supernatant	X		X	X		X	X		X	X	X

 Active TB participants with Microbiological Confirmation of TB (defined as smear+, Xpert+, or smear negative but cultured confirmed. Patients who are initially negative by smear and/or Xpert will be enrolled if they meet criteria for Cat-1 TB treatment. Participants who remain culture negative by 3 months will be follow-up but will not be included in the primary analysis.

 An additional 'End of Rx' time-point to be observed for participants with Rx duration exceeding 6 months

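### The Aim 1 claim of at least 90% power for relative risks from 1.5 at 10–40% prevalence is not met by its own inputs; at a 24-month risk ratio of 1.5, power is about 52–82%

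*Protocol*

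**What the plan says.** Section 9.1 of the protocol sets the primary analysis of Aim 1: "The primary analysis set will be 800 adult PTB patients". On the event count it says "we expect 20% (n=160) of 800 adult PTB cases will have the composite primary outcome", built up as "2% will fail, 6% will die, and 12% will have recurrence". The power claim follows: "This study will have at least 90% power at 5% level of significance", for host and microbial risk factors "with a prevalence of 10% - 40%, associated with poor treatment outcomes with relative risk ratio ranging from 1.5 to 6.0 over 24 months". It does not say whether the test is one- or two-sided. It does not tie particular relative risks to particular prevalences, and it makes no allowance for losses. The planned analysis is an adjusted Poisson regression with person-years as offset, follow-up ending at the event.

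Two other places bear on the inputs:

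- Section 2.2 puts the cured share at about 85% and says that "approximately 12% of cured patients develop recurrent TB within 18 months of treatment".
- Footnote 1 to the schedule of evaluations for the Active TB cohort (Table 1 in section 6) says "Participants who remain culture negative by 3 months will be follow-up but will not be included in the primary analysis".

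**The concern.** Read plainly, the sentence promises 90% power for every combination in the stated ranges, including a relative risk of 1.5 at 10% prevalence. With 160 events in total, an exposure carried by 80 of 800 patients yields only about 23 exposed events, too few for that promise.

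This is the protocol's only numerical power claim; the Aim 2 power paragraph gives expected case counts and no power. The study is meant to show which factors deserve priority for public health action. A non-significant result for a factor with a true relative risk near 1.5 could be taken as evidence against it, on the strength of a 90% figure that the design does not deliver. Section 2.2 itself cites a pooled relative risk of 1.89 for diabetes and mortality, so effects of this order are the ones at issue.

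**Working it through.** **Inputs.** From section 9.1: N = 800, overall risk 20% (160 events), prevalence q from 10% to 40%, RR = 1.5, 5% level. Two-sided testing is my assumption; one-sided is tried below.

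**The plan's own figures.** The event count reproduces: 2% + 6% + 12% = 20%, and 0.20 × 800 = 160. The 90% does not.

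**1.5 as a 24-month risk ratio.** Unexposed risk p0 = 0.20/(1 − q + 1.5q); exposed risk p1 = 1.5 × p0; n1 = 800q; n0 = 800(1 − q). Power = Φ[((p1 − p0) − 1.96·s0)/s1], with s0 = √[0.20 × 0.80 × (1/n1 + 1/n0)] and s1 = √[p1(1 − p1)/n1 + p0(1 − p0)/n0].

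- q = 10%: p0 = 0.1905, p1 = 0.2857, s0 = 0.0471, s1 = 0.0526. Power 52%.
- q = 40%: p0 = 0.1667, p1 = 0.2500, s0 = 0.0289, s1 = 0.0296. Power 82%.

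**The planned person-years Poisson model.** Because follow-up stops at the event, a 24-month risk ratio of 1.5 corresponds to a rate ratio of about 1.58–1.59 under a constant hazard. Simulating that model (20,000 runs per prevalence) gives about 53%, 72%, 79–80% and 82%, almost the same as the two-proportion test.

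**1.5 as a rate ratio.** Power ≈ Φ[ln 1.5/√(1/E1 + 1/E0) − 1.96], where E1 and E0 are the exposed and unexposed events.

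- q = 10%: E1 = 22.9, E0 = 137.1, SE = 0.226. Power 43%.
- q = 40%: E1 = E0 = 80, SE = 0.158. Power 73%.

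| Prevalence | 10% | 20% | 30% | 40% |
|---|---|---|---|---|
| Power, risk ratio 1.5 | 52% | 71% | 79% | 82% |
| Power, rate ratio 1.5 | 43% | 63% | 71% | 73% |
| Risk ratio detectable at 90% | 1.89 | 1.68 | 1.61 | 1.58 |
| Rate ratio detectable at 90% | 1.95 | 1.75 | 1.68 | 1.67 |

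**More favourable readings** (two proportions, RR 1.5, prevalence 10/20/30/40%):

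- One-sided 5%: 63/80/87/89%.
- 20% as the risk in the unexposed, which contradicts 160 events overall: 54/76/86/90% (89.6% before rounding at 40%).
- Both together: 65/84/91/94%.

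None reaches 90% over the whole range.

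**Expected events.** If only the cured 85% are at risk of recurrence: 0.12 × 0.85 = 10.2%, and 2% + 6% + 10.2% = 18.2%, or 0.182 × 800 = 145.6, about 146 events. If all who neither fail nor die (92%) are at risk: 0.12 × 0.92 = 11.04%, total 19.04%, about 152 events. With 146 events, power at RR 1.5 is 48–77% (risk ratio) or 40–69% (rate ratio) across 10–40% prevalence, a fall of about 3–5 points.

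**Primary analysis set.** Section 9.1 makes the 800 adult pulmonary cases the primary set. Footnote 1 takes out participants still culture negative at 3 months. Section 5.2 already limits pulmonary TB to smear- or Xpert-positive cases, or smear-negative cases culture-confirmed by 12 weeks. The overlap in dispute is therefore mainly the smear- or Xpert-positive patients whose culture is negative, whom section 5.2 keeps in follow-up.

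**The case against.** The strongest defence of the sentence is that it lists ranges rather than a full grid, so that 1.5 may be meant only for the commonest exposures. That does not rescue it: at 40% prevalence two-sided power is still 82%, or 73% on the rate scale. The pairing would also put 6.0 at 10% prevalence, where about 1.9 is already detectable. It is also fair that this is an observational cohort reporting rate ratios with confidence intervals, so a careful reader would judge a null result by its interval. That limits the harm but does not make the stated power correct.

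Several stronger readings are tempting, and the documents do not support them.

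- **One span of 43–82%.** This would join a rate-ratio figure to a risk-ratio figure. Each scale has its own range, 43–73% or 52–82%.
- **160 events must become 146.** The denominator slip is real, but 18.2% is not forced. The failure and death figures in section 2.2 rest on smear positivity at 5 months and on deaths during treatment. Section 8 counts any positive culture by the end of therapy, clinical failure, and death within 24 months of starting treatment. It also counts bacteriologic recurrence among all who did not fail. The true count could be nearer 160.
- **800 is too large by a known amount.** No number of culture-negative exclusions is forecast. The 5% in section 5.2 triggers a feasibility review; it is not an expectation.
- **HIV falls outside the claim.** Section 2.2 says "only 2-15% of Indian patients with TB have HIV co-infection", but the power sentence promises nothing below 10% prevalence, and the two ranges overlap. This is not an error.

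**Conclusion.** Wrong as written. On the section's own 800 patients and 160 events, no prevalence from 10% to 40% gives 90% power at a relative risk of 1.5 with a two-sided 5% test. The shortfall is about 8 to 38 percentage points on the risk-ratio scale and 17 to 47 on the rate-ratio scale. Across the whole prevalence range, the claim holds only from a risk ratio of about 1.9, or a rate ratio of about 1.95, upwards.

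The result assumes a single binary exposure, complete follow-up and no covariate adjustment. Adjustment and losses would normally lower power further; neither was computed. The agreement between the two-proportion test and the person-years model assumes a constant hazard.

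The recurrence denominator is a lesser inconsistency that moves power by a few points. The disagreement over culture-negative patients is a separate matter of wording, and its numerical effect cannot be derived from the protocol.

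**What to change.** 1. In section 9.1, replace the Aim 1 power sentence with the smallest relative risk detectable at 90% power, stating the scale and that the test is two-sided 5%. With 160 events, at 10%, 20%, 30% and 40% prevalence, this is about 1.9, 1.7, 1.6 and 1.6 (risk ratio) or 1.95, 1.75, 1.7 and 1.7 (rate ratio). Add that power at a risk ratio of 1.5 is about 50–80%, before adjustment and losses.
2. Either restate the expected events with the recurrence denominator made explicit (about 146 or about 152, as worked above), or keep 20% and justify it from the protocol's broader failure and 24-month death definitions. If the count changes, recompute item 1.
3. Reconcile section 9.1 with footnote 1 of the Active TB schedule so that both name one primary analysis set, say where smear- or Xpert-positive, culture-negative adults belong, and base the power statement on that set.

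The cost is protocol wording and a short recalculation. No extra patients or procedures are needed; the stated power becomes less favourable.

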### **2.3. FACTORS ASSOCIATED WITH PROGRESSION TO ACTIVE TB DISEASE**

Many of the above-mentioned potentially modifiable factors have been associated with progression to active TB, but their relative independent and combined contributions towards risk of active TB disease has not been well studied, particularly in India. HIV increases the risk of reactivation of latent MTB infection by up to 100 times and increases the risk of progression to active disease in those who acquire new MTB infection [40]. Other less potent but more common risk factors including DM, under nutrition, smoking and alcohol misuse have been associated with 2-3 times increased risk of development of active TB [41- 43].

Non-modifiable host factors such as age, sex, and host genetics may also be influential. Disease risk after primary infection is highest in children < 4 years, then decreases until age 10, after which a second peak starts and is noted through reproductive age until 34 years in women but is more sustained in men until age of 50 years [44]. These age- and sex-specific differences also impact the presentation of disease where young children are more likely to have disseminated disease while women are more likely than men to have EPTB. The mechanisms for these differences are unknown. Host genetic polymorphisms and host proteins may also be associated with risk of developing active TB, [45, 46] but it is unknown what the prevalence or association is of LTR4 genetic variants or PGYRP or NOD proteins with risk for developing active TB. Microbial strain lineage may also matter. A study among Gambian TB patients and their household contacts found that progression to active TB but not transmission varied by MTB lineage with *M.africanum* causing lower proportion of active TB disease than other MT strains [38]. Further,

strain lineage has differing phylogeography, where India, sub-Saharan Africa and the Americas each have different predominant strain lineages [37]

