### 3. Objectives

The study will establish and maintain 3 prospective cohorts -- adults and children with active TB disease (**1.Active TB Cohort**), adults and children at high risk for developing active TB (**2.Household Contacts Cohort**), and adult and children controls who do not have any known exposure to TB (**3. Control Cohort**) to address our 3 specific aims-

**Aim 1:** To measure the host and microbial factors associated with treatment outcomes in Indian adults and children

**Aim 2:** To investigate the host & microbial factors associated with progression from infection to active TB disease in Indian adults and children

**Aim 3:** To explore the host and microbial factors associated with MTB transmission

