**HOUSEHOLD CONTACTS COHORT (ALL MUST APPLY)**

- i. All adults and children living in the same house as the adult (>18yrs) active Pulmonary TB participant during the 3 months prior to diagnosis of TB.
- ii. Ability of participant/legal guardian to provide informed consent/assent

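### The Aim 2 model is run on all 3200 household contacts, infected or not, so it estimates TB incidence in contacts and not, as Section 9.1 says, progression from infection

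*Protocol*

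**What the plan says.** Section 3 of the protocol gives Aim 2 as: "To investigate the host & microbial factors associated with progression from infection to active TB disease in Indian adults and children".

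Section 9.1 fixes the population: "The analysis set is individuals in the HH Contact Cohort: 3200 HH contacts of 800 PTB patients". The outcome is active TB within 24 months, and the model is a Poisson regression with the index case as random effect. The parameter is named as follows: "The association between host and microbial factors with progression from infection to active TB disease will be estimated using random effects".

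Cohort B entry (Section 5.2) rests on household residence and consent: "All adults and children living in the same house as the adult (>18yrs) active Pulmonary TB participant during the 3 months prior to diagnosis of" the disease. No TST or QGIT result is required.

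The Aim 2 power paragraph states: "We estimate that at least 40% (n=1280) will be latently infected". It continues: "We estimate that 320 (25%) of them would be recently infected and have a 15% 2 year risk of developing active TB". It adds background TB of 0.37% per year regardless of infection, and reaches 72 cases. On follow-up: "We expect approximately 3200 HH contacts will be followed for an average duration of 2 years".

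Table 2 schedules TST and QGIT at entry and, if the previous result was negative, at 4, 12 and 24 months. QGIT is also scheduled at the active TB visit. The objectives table in Section 3 lists, under Aim 2, a study of progression risk by TST/QGIT status, and separately a study of modifiable risk factors for developing active TB. New infection is the primary outcome of Aim 3 (Sections 8 and 9.1).

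**The concern.** In a set of infected and uninfected contacts, the risk of TB combines the chance of being or becoming infected with the chance of progressing once infected. Aim 2 asks about the second. The model in Section 9.1 sees only the combination, because neither 8.2 nor 9.1 brings infection status into it. A host, household or strain factor that acts on infection alone can therefore appear as a progression factor, and one that acts in opposite directions on the two steps can be masked.

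The protocol itself treats the steps as distinct. Infection has its own aim, and Section 2.4 notes that many of the same factors bear on transmission with possibly different weight. Section 2.6 intends the results to guide which factors public health programmes address first, so attributing an effect to the wrong step matters.

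**Working it through.** **Inputs (Section 9.1, Aim 2 Power).** 3200 contacts; 40% infected; 25% of those recently infected; 15% two-year risk in the recently infected; background 0.37% per year for everyone; 2 years of follow-up.

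**The plan's own figure.**
- Infected: 3200 × 0.40 = 1280. Uninfected: 1920, an upper bound because the plan says at least 40% are infected.
- Recently infected: 1280 × 0.25 = 320, or 10% of all contacts. Remotely infected: 960, or 30%.
- Cases from recent infection: 320 × 0.15 = 48.
- Background: 3200 × 0.0037 × 2 = 23.7.
- Total 71.7, which reproduces 72.

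**Where the risk lies.** The recently infected carry 0.15 + 0.0074 = 15.74% over two years. Everyone else, including the remotely infected, carries 0.74%.

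**A factor with no effect on progression that multiplies recent infection by k.** Assumptions: without the factor, 10% are recently and 30% remotely infected; the factor leaves remote infection unchanged; k is my choice, as the protocol gives no such figure.
- All contacts: RR = (0.0074 + 0.15 × 0.10k) / (0.0074 + 0.15 × 0.10) = (0.0074 + 0.015k) / 0.0224.
- Infected only: the recent share is 0.10k / (0.10k + 0.30), against 0.25 without the factor. RR = (0.0074 + 0.15 × share) / 0.0449.

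| k | All contacts | Recent share of infected | Infected only |
|---|---|---|---|
| 1.25 | 0.02615/0.0224 = 1.17 | 0.294 | 1.15 |
| 1.5 | 0.0299/0.0224 = 1.33 | 0.333 | 1.28 |
| 2 | 0.0374/0.0224 = 1.67 | 0.400 | 1.50 |

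The effect on progression is 1.0 in every row.

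**A factor with no effect on progression that raises remote infection 1.5-fold (30% to 45%), recent infection unchanged at 10%.** All contacts: RR 1.00, since remote infection carries only background risk. Infected only: the recent share falls to 0.10/0.55 = 0.182, so RR = (0.0074 + 0.15 × 0.182) / 0.0449 = 0.77. Restriction creates a spurious protective effect.

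**Expected cases.**
- Infected contacts: 48 + 1280 × 0.0074 = 57.5. Uninfected: 1920 × 0.0074 = 14.2, or 14.2/71.7 = 20% of the total.
- SE ratio after restriction: √(71.7/57.5) = 1.12.
- Mean follow-up of 2 years equals the 24-month maximum, so 72 allows no loss. With an assumed 10% and 20% loss of person-time: 71.7 × 0.9 = 65 and 71.7 × 0.8 = 57 overall; 57.5 × 0.9 = 52 and 57.5 × 0.8 = 46 in the infected.

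**The case against.** **Partly handled already.** The objectives table lists a study of progression risk by TST/QGIT status and words the risk-factor study as development of active TB, which an all-contact model does answer. Section 8 gives the primary outcome as incident TB. Covariates may be left to a statistical analysis plan that is not shown. This has weight, but the listed study is not tied to the Section 9.1 model, and the protocol itself fixes the set and names the parameter. Those two do not match.

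**Stronger readings a reader might infer, which the documents do not support:**
- *That restricting to infected contacts solves the problem.* This follows only if all infected contacts share one risk: 57.5/1280 = 4.49%, against 0.74% in the uninfected. On that footing a shift in infection from 35% to 50% gives 1.27 in all contacts, a shift from 30% to 60% gives 1.60, and restriction returns 1.0. Section 9.1 instead places all the excess risk in the 320 recently infected, and those shifts appear nowhere in the protocol.
- *That the two steps cannot be separated in this cohort.* TST and QGIT are scheduled for all contacts, so infection status can enter the model within the 3200.
- *That the lineage study in Section 2.3 shows the bias.* It found that "progression to active TB but not transmission varied by MTB lineage". A factor that leaves infection unchanged gains no spurious effect from the all-contact set.
- *That the study would report causes.* The protocol speaks of association throughout.

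The full-retention assumption is a separate weakness of the case projection and adds nothing to the mismatch itself.

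**Conclusion.** The point holds as a mismatch between the named parameter and the analysis set. As written, the Aim 2 model estimates TB incidence among household contacts, not progression from infection. Only factors related to infection are affected. For a factor that multiplies recent infection by 1.25 to 2 and does nothing to progression, the all-contact RR is about 1.17 to 1.67. That range rests on the plan's 40%, 25%, 15% and 0.37% figures and on assumed multipliers.

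Restriction alone leaves about 1.15 to 1.50, because TST/QGIT positivity at entry mixes recent and remote infection, and it can push factors linked to remote infection below 1. No available analysis removes this fully, so a residual limit has to be stated. The point should be fixed, but it does not undermine the design: the data needed are already scheduled.

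**What to change.** 1. In Section 9.1, name the all-contact estimate as incident TB among household contacts, and drop the claim that it estimates progression from infection.
2. Add a pre-stated Aim 2 progression analysis using the TST/QGIT results at entry, 4, 12 and 24 months. Either analyse contacts with evidence of infection, or keep all contacts with infection status as a stratum or time-updated covariate. Adjust for measured household exposure. Report entry-positives and converters separately, as an imperfect proxy for remote and recent infection. State a rule that keeps contacts who first test positive at the TB diagnosis visit; otherwise they contribute no infected person-time. Base conclusions about progression on this analysis and state its residual limit.
3. Restate the expected cases: about 72 only if every contact completes 24 months, about 65-57 with an assumed 10-20% loss of person-time, and about 57 in infected contacts before loss (52-46 after).

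Cost: wording and analysis specification, with no new visits or tests. The infected-contact analysis has about 20% fewer events and an SE about 12% larger. Some infection status will be misclassified, because conversion is seen only at scheduled visits.
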